A multi-center, randomized, 36-month, parallel-group, non-inferiority, phase III study to compare the effectiveness of 500 mcg QD or alternate regimen of roflumilast (Daliresp) therapy versus 250 mg QD, 500 mg QD three times per week, or alternate regimen of azithromycin therapy to prevent COPD exacerbations (RELIANCE)

Protocol Version 4.0

08 June 2020

Funded by PCORI PCS-1504-30430

Protocol Version 4.0

RELIANCE is a U.S.-based pragmatic clinical trial funded by the Patient-Centered Outcomes Research Institute (PCORI) to compare long-term use of roflumilast vs. azithromycin in up to 3,200 patients. It is intended to support hospital efforts to reduce the risk of all-cause hospitalization and reduce pre-mature deaths in individuals with chronic obstructive pulmonary disease (COPD). The COPD Patient Powered Research Network (PPRN) and affiliated investigators will conduct the trial in sites in the U.S.

Both roflumilast and azithromycin have been shown to reduce the risk of COPD exacerbations compared to placebo. However, there has not been a head-to-head comparison of the two medications. So, the relative harms and benefits of the two medications are unknown. Eligible patients will be randomized (1:1) to receive either a prescription for roflumilast or a prescription for azithromycin and will be followed for at least 6 and up to 36 months. The primary endpoint is the combined outcome of all-cause hospitalization or death; the secondary endpoints include premature treatment discontinuation, patient-reported adverse effects, and physical, social, and emotional health. Patients will provide data via an online Participant Portal or via a call center. Baseline and outcome data will also be collected from site medical records and administrative/claims databases.

Protocol Version 4.0

PICOTS table


Population N=up to 3,200 randomized over 30 months
	
Inclusion criteria (must meet all criteria):
 
 (1) Patient and treating clinician considering treatment intensification with roflumilast or azithromycin to reduce the risk of COPD exacerbations; (2) Age ≥ 40 years; (3) Current or past smoker of at least 10 pack years; (4) Diagnosis of severe COPD and associated chronic bronchitis; (5) Hospitalized with a diagnosis of COPD exacerbation in the past 12 mos; (6) Current medications include inhaled LAMA, ICS/LABA, or LAMA/LABA; (7) English- or Spanish-speaking. (8) Willing and able to provide a contact telephone number. 
Exclusion criteria (any criterion):
 
 (1) Unable or declines to provide informed consent; (2) Declines to provide social security number (SSN), health insurance claims number, or Tax Payer ID Number (as applicable); (3) History of intolerance to azithromycin or roflumilast that the patient or patient's treating clinician considers sufficiently serious to avoid either treatment option; (4) Current treatment with long-term (more than 30 days) roflumilast or azithromycin (previous treatment with 1 or more doses of azithromycin or roflumilast is not an exclusion criterion, as long as the patient and clinician are seeking treatment intensification options); (5) Known hypersensitivity to azithromycin, erythromycin, any macrolide or ketolide antibiotic; (6) History of cholestatic jaundice/hepatic dysfunction associated with prior use of azithromycin; (7) Moderate to severe liver impairment (Child-Pugh B or C); (8) Current pregnancy; (9) Any other clinician-determined clinical exclusion as per their clinical practice.

Intervention
	
Prescription for Azithromycin (250 mg/day, or 500 mg three times per week, or alternate regimen) x 6 to 36 months

Comparator
	
Prescription for Roflumilast (250 mcg/day x 4 weeks, then 500 mcg/day or alternate regimen) x 6 to 36 months

Protocol Version 4.0


Outcomes
	
Primary outcome: All-cause hospitalization or death collected primarily by data provided by patients via the Patient and Call Center Portals, and review of electronic health records (I). Administrative and claims data will be reviewed to evaluate the completeness of ascertainment of the primary outcome. Trial data and National Death Index (NDI) will contribute to primary analyses of primary and secondary outcomes. Trial data, NDI, and Medicare data will contribute to secondary analyses of primary and secondary outcomes.
 
Secondary outcomes:
 
 • All-cause individual events: hospitalization, emergency department visit, urgent care visit, death (source: Participant Portal, Investigator Portal/EHR, Medicare claims data in a subset, NDI) • Patient-reported outcomes (source: Reference Table: PRO Common Measures, 3.1, Oct 25, 2014) PROMIS measures using the NIH-PROMIS instruments (source: Call Center or Participant Portal): 
 1. Physical function (Domain: Physical function (alternate), Item code: GLOBAL 06, Item bank: PROMIS Global) 2. Problems with sleep (Domain: Sleep disturbance, Item code: SLEEP20, Item bank: PROMIS Sleep Disturbance) 3. Fatigue (Domain: Fatigue, Item code: 2876R1, Item bank: PROMIS Peds - Fatigue) 4. Anxiety (Domain: Anxiety, Item code: EDANX53, Item bank: PROMIS Emotional Distress-Anxiety) 5. Depression (Domain: Depression, Item code: PEDGLOBAL2, Item bank: PROMIS Peds - Global) • Adverse events: patient report for hearing decrement, diarrhea, nausea, suicidal ideation, other (source: self-report via Call Center or Participant Portal); microbiology cultures in which macrolide-resistant organisms were identified in sputum (sole: EHR) • Medication adherence (source: self-report via Call Center or Participant Portal; Medicare claims data in a subset) • Crossover to alternate study medication (source: self-report via Call Center or Participant Portal, query of clinic staff; Medicare claims data in a subset) • Treatment discontinuation (source: self-report via Call Center or Participant Portal; query of clinic staff; Medicare claims data in a subset) • Out-of-pocket costs for roflumilast or azithromycin (source: self-report via Call Center or Participant Portal) • Weight (source: self-report via Call Center or Participant Portal)

Timing
	
 • Every participant will be followed for a minimum of 6 months 
 ○ Patients will receive a phone call 1 week after randomization, then will complete follow-up at 3 and 6 months after randomization, then, every 6 months until the patient achieves a primary outcome.

Setting
	
Patients will be identified as they seek care with their clinician (outpatient clinic, telemedicine visit, or hospital)

Study design
	
Pragmatic, non-inferiority trial using an intention-to-treat analysis to evaluate whether daily azithromycin is non-inferior to daily roflumilast in patients at high risk of COPD exacerbations. We will randomize individual patients to receive prescriptions for roflumilast or azithromycin (1:1 ratio), stratified by site and current smoking status (yes/no).

Protocol Version 4.0

Contents

1. Study Overview6

 1.1. Rationale.....6

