The FDA approved labeling for roflumilast³⁸ includes a section on “Warnings and Precautions” that discusses concerns about psychiatric events, including suicidality. Treatment with roflumilast is associated with an increase in psychiatric adverse reactions. In 8 controlled clinical trials 5.9% (263) of patients treated with roflumilast 500 mcg daily reported psychiatric adverse reactions compared to 3.3% (137) treated with placebo. The most commonly reported psychiatric adverse reactions were insomnia, anxiety, and depression, which were reported at higher rates in those treated with roflumilast 500 mcg daily (2.4%, 1.4%, and 1.2% for roflumilast versus 1.0%, 0.9%, and 0.9% for placebo, respectively). Instances of suicidal ideation and behavior, including completed suicide, have been observed in clinical trials. Before using roflumilast in patients with a history of depression and/or suicidal thoughts or behavior, the FDA-approved Prescribing Information suggests that clinicians should carefully weigh the risks and benefits of treatment with roflumilast in such patients. Patients, their caregivers, and families should be advised of the need to be alert for the emergence or worsening of insomnia, anxiety, depression, suicidal thoughts or other mood changes, and if such changes occur to contact their healthcare provider. Prescribers should carefully evaluate the risks and benefits of continuing treatment with roflumilast if such events occur.

OPTIMIZE was a 12-week randomized double-blind clinical trial in 1,321 patients with severe COPD associated with chronic bronchitis that was used to determine if starting a lower dose

Protocol Version 4.0

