of roflumilast could reduce all-cause treatment discontinuation at 12 weeks.³⁹ Results of OPTIMIZE indicate that roflumilast 250 mcg per day for the first 4 weeks (then 500 mcg per day X 8 weeks) was associated with a significantly lower risk of all-cause treatment discontinuation than roflumilast 500 mcg per day X 12 weeks (odds ratio 0.66, 95% CI 0.47 to 0.93, $p=0.017$) and lower rates of adverse events such as diarrhea, nausea, headache, decreased appetite, insomnia, and abdominal pain (odds ratio 0.63, 95% CI 0.47 to 0.83, $p=0.001$). Initiating roflumilast at 500 mcg every other day X 4 weeks, followed by 500 mcg per day X 8 weeks was associated with a numerically lower, but not significantly different, risk of all-cause treatment discontinuation compared with 500 mcg per day X 12 weeks (20.1% vs. 24.6%, $p=0.11$).³⁹ Findings showed the same pattern when comparing treatment emergent adverse effects, adverse events were lower in the groups starting at lower doses of roflumilast versus the group that started at 500 mcg per day dose; for comparison of 250 mcg per day vs 500 mcg per day the rates of treatment emergent adverse events were 45.4% vs 54.2% ($P=0.001$), respectively, and 48.3% vs 54.2% ($P=0.09$) for the comparison of 500 mcg every other day vs 500 mcg per day. These results indicate that treatment discontinuations due to adverse effects can be reduced by starting with a lower initial dose of roflumilast. The harms of chronic azithromycin and roflumilast therapy when used in routine clinical settings are not well understood. The RELIANCE study seeks to compare the harms of both medications in “real-world” clinical settings.

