1.2. Research Design

The aims of the RELIANCE study are:

[figure not shown]
1. Primary aim: To conduct a pragmatic, randomized clinical trial in a high-risk population of patients with COPD and chronic bronchitis to test the hypothesis that azithromycin is non-inferior to roflumilast for prevention of all-cause hospitalizations or death (a primary composite outcome).

Secondary effectiveness outcomes include all-cause individual events (urgent care visits, emergency department visits, hospitalizations, and death) and other patient-reported measures of physical, mental, and social health.

2. Secondary aim 1: Conduct analyses to evaluate the potential for heterogeneity of treatment effects in current versus former smokers
3. Secondary aim 2: To compare the tolerability of azithromycin vs. roflumilast as assessed by patient-reported adverse events; adherence to assigned treatment (patient-report and claims data); crossover to alternate treatment group (patient-report, query of clinic staff, and claims data); treatment discontinuation (patient-report, query of clinic staff, and claims data); out-of-pocket costs (patient-report); and weight (patient-report).

The trial is a parallel, pragmatic non-inferiority trial with two treatment groups, azithromycin and roflumilast (Figure 1). Up to 3,200 participants will be randomized (1:1) to receive a prescription for one of the two treatments. Treatment assignments will be stratified by site and smoking status (former versus current) using a permuted block design with multiple block sizes. Treatment assignments will be concealed prior to randomization. Once a patient is assigned to receive a treatment, the clinician, Site Coordinator and patient will all be unmasked, i.e., know the treatment.

Figure 1

Protocol Version 4.0

[figure not shown]

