Site Coordinators will be asked to assist in locating patients who are lost to follow-up and in ascertaining or verifying hospitalizations and death. Site Coordinators will also submit data on patient outcomes, such as adverse events, all-cause hospitalization, changes to study medications, medical diagnoses, or other relevant information, and microbiology cultures in which macrolide-resistant organisms were identified in sputum from the EHR via ad hoc and end-of-study reports on the Investigator Portal ([Table 3](#)). We will ascertain vital status on all patients via the NDI after follow-up is completed.

In addition, we will work with the FDA Sentinel Operations Center (SOC) to obtain Medicare data regarding the claims for study medications and healthcare utilization for patients enrolled in Medicare.

Protocol Version 4.0

Data item	Sources (and estimated time for patients)	Baseline (BL)	1 week	3 and 6 mos after randomization, then every 6 mos until primary outcome is recorded or 36 months after start of enrollment, whichever occurs first.	End of study
Informed consent	Investigator Portal	X			
Demographics	Investigator Portal (3 min)	X			
Smoking status	Investigator Portal	X			
	Participant Portal/Call Center (2 min)			X	
PROMIS questionnaires (physical function, sleep disturbance, fatigue, anxiety, depression)	Investigator Portal	X			
	Participant Portal/Call Center (2 min)		X (if not done at BL)	X	
Height, weight	Investigator Portal	X			
	Participant Portal/Call Center (2 min)			X	
Study treatment (adherence, treatment discontinuation, cross-over to alternate medication)	Investigator Portal	X			
	Participant Portal/Call Center (3 min)		X	X (and ad hoc)	
	Claims databases				X
Out-of-pocket costs	Participant Portal/Call Center (2 min)		X	X	
Healthcare utilization	Investigator Portal	X			X
	Participant Portal/Call Center (5 min)		X	X (and ad hoc)	
	Claims databases				X
	National Death Index				X
Adverse events (hearing decrement, diarrhea, nausea, suicidal ideation)	Participant Portal/Call Center (3 min)		X	X (and ad hoc)	
	Claims databases				X
Adverse event (microbiology cultures of macrolide resistant organisms in sputum)	Investigator Portal				X

Protocol Version 4.0

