Macrolides (including azithromycin) are known to cause ventricular arrhythmias that could be fatal, but the incidence for long-term azithromycin use to prevent COPD exacerbations is unknown. On the basis of results published in an observational study using claims data, the FDA re-iterated the importance of carefully reviewing patient-level risk factors (history of prolonged QT interval, comorbid condition, or arrhythmogenic potential of other co-therapies) when using azithromycin.^{60,61} The incidence of arrhythmias with macrolides in the absence of additional risk factors is estimated to be very low, perhaps <1 in 100,000 individuals.

In a Cochrane review of placebo-controlled efficacy trials of roflumilast, premature treatment discontinuation due to adverse effects was more common with roflumilast than with placebo (15 vs. 9%, $p<0.05$; 9,511 patients).²⁸ The most common adverse effects that were also more common in the roflumilast group included diarrhea (10 vs. 3%, $p<0.05$), nausea (5 vs. 1%, $p<0.05$); weight loss (8 vs. 2%, $p<0.05$), psychiatric disorders (7 vs. 4%, $p<0.05$; includes anxiety, depression); and sleep disturbances/insomnia (3 vs. 1%, $p<0.05$). Mortality was low in the trials of roflumilast, with no significant difference between groups (roflumilast vs. placebo: 2 vs. 2%). A similar increase in adverse effect-associated treatment discontinuation was noted in comparative trials of up to 12 months in the REACT, RESPOND² and M2-124 and M2-12533 studies (12 vs. 8% placebo). The most common adverse effects that were also more common in the roflumilast group included diarrhea (17 vs. 6% placebo), weight loss (9 vs. 3% placebo). The OPTIMIZE study found that premature treatment discontinuation can be reduced by initiating treatment with a 4-week course of 250 mcg/day of roflumilast before dose-escalation to 500 mcg/day.

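### The harms comparison leaves the gravest harms the protocol names, ventricular arrhythmia and suicidal behavior, counted by arm only inside all-cause hospitalization and death; a short claims code list would add a descriptive count

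*Protocol*

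**What the plan says.** **Purpose.** Section 1.1 states: "The RELIANCE study seeks to compare the harms of both medications", in real-world clinical settings. The protocol's opening summary calls the relative harms of the two drugs unknown.

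**Named serious harms.**
- For azithromycin, Section 4.3 says "Macrolides (including azithromycin) are known to cause ventricular arrhythmias that could be fatal" and that the incidence in long-term use for COPD is unknown. It adds that the incidence "in the absence of additional risk factors is estimated to be very low, perhaps <1 in 100,000 individuals". Section 1.5 repeats the QT warning.
- For roflumilast, Section 1.1 says "Instances of suicidal ideation and behavior, including completed suicide, have been observed in clinical trials". It also reports that 5.9% (263) of patients on 500 mcg daily "reported psychiatric adverse reactions compared to 3.3% (137) treated with placebo". It gives no rate for suicide or suicide attempt.

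**What is compared.**
- The Outcomes row of the PICOTS table lists "Adverse events: patient report for hearing decrement, diarrhea, nausea, suicidal ideation, other", by self-report, together with EHR records of macrolide-resistant sputum cultures.
- Secondary aim 2 in Section 1.2 is "To compare the tolerability of azithromycin vs. roflumilast as assessed by patient-reported adverse events", with adherence, crossover, discontinuation, cost and weight.
- The Table 3 row that lists claims as a source for adverse events begins "Adverse events (hearing decrement, diarrhea, nausea, suicidal ideation" and names no other event.
- Hospitalization and death appear as all-cause events only. Sections 2.2, 3.4 and 4.2 describe the National Death Index as a source of vital status and unreported deaths.

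**The concern.** A patient cannot report their own fatal arrhythmia or completed suicide. The adverse-event outcome is mainly self-report, and its claims source is tied to the same symptoms. The remaining compared outcomes, all-cause admission and all-cause death, contain these events but do not identify them.

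Followed as written, the trial could report non-inferiority and a tolerability comparison without saying how many arrhythmic or suicidal events occurred in each arm. The low arrhythmia figure in Section 4.3 holds only without additional risk factors. The protocol lists no QT, arrhythmia or psychiatric exclusion and leaves these to the clinician, so the low figure need not describe the patients enrolled.

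**Working it through.** **1. Reproduce the plan's figures.** Inputs from Section 3.1: 3,200 patients, 30% with an event at 1 year, 5% loss per year, 30 months' accrual plus 6 months, margin 1.2, one-sided 0.025.
- Event hazard λ = −ln(0.70) = 0.3567 per year; loss hazard μ = −ln(0.95) = 0.0513 per year; h = λ + μ.
- With uniform accrual, P(event) = (λ/h) × [1 − (e^(−0.5h) − e^(−3h))/(2.5h)] = 0.4273.
- 3,200 × 0.4273 = 1,367 events; Section 3.5 gives 1368.
- Power = Φ(ln 1.2/√(4/1368) − 1.96) = 92.1%; Section 3.1 gives 92%.

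Nothing in the sample-size calculation is in dispute.

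**2. Can the composite stand in?** Take 684 events per arm and add x events to one arm of 1,600. The hazard ratio is approximated by (684 + x)/684, with SE = √(4/(1368 + x)). The excess rates are assumptions.

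| Assumed excess | x | HR if on azithromycin | HR if on roflumilast | Chance of two-sided p < 0.05 |
|---|---|---|---|---|
| 0.1% | 1.6 | 1.002 | 0.998 | 5.0% |
| 0.2% | 3.2 | 1.005 | 0.995 | 5.1% |
| 0.5% | 8 | 1.012 | 0.988 | 5.5% |
| 1% | 16 | 1.023 | 0.977 | 7.1% |

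Solving x = 684 × (exp(1.96 × √(4/(1368 + x))) − 1) gives about 74 extra events, or 74/1,600 = 4.6% of an arm, before the composite itself would differ significantly.

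**3. Can all-cause death stand in?** Suppose every excess event is fatal. With d background deaths per arm, SE = √(1/d + 1/(d + x)). Section 1.1 gives 1-year mortality of 7% to 50%, so d = 112 to 800. Across excesses of 0.1% to 1%, power is 5% to 18% at d = 112 and 5% to 7% at d = 800.

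**4. What could a separate count show?**
- At 1 in 100,000, the expected number is 1,600/100,000 = 0.016 per arm.
- Zero events in n patients gives a one-sided 95% upper limit of 1 − 0.05^(1/n): 0.19% for n = 1,600. If claims cover an assumed 50% to 90% of an arm, the limit from claims alone is 0.37% to 0.21%.
- Newcombe 95% intervals for the difference, 1,600 per arm: 0 vs 0, ±0.24 points; 4 vs 4, ±0.42; 8 vs 8, ±0.54; 16 vs 16, ±0.73; 24 vs 8, 0.31 to 1.76.

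Even 0 vs 0 does not exclude an excess of 0.1% or 0.2%. The count can bound or reveal only a large difference.

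**5. How complete would capture be?** Scheduled queries stop at the first primary event. Expected person-years to first event or loss are 3,200 × 0.4273/0.3567 ≈ 3,834, against 3,200 × 1.75 = 5,600 potential, or 68%. Events after the first admission would be captured less completely.

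**The case against.** **Coverage elsewhere.** The adverse-event item includes suicidal ideation and an open category. PROMIS anxiety, depression and sleep items are compared. Section 2.2 has sites submit adverse events and medical diagnoses, and Section 3.4 has them review the EHR for unreported events. Section 4.1 asks clinical leads to report adverse events. Section 4.7 gives the DSMB data grouped by treatment, and it may terminate for safety. All-cause death is its own secondary outcome with vital status on everyone. This stands as partial coverage. A reader might infer that the trial would be blind to these harms; the documents do not support that. What is missing is a compared, attributed count.

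**The SAP or forms may supply it.** The SAP is not shown, and site forms may already carry a diagnosis. That is fair, and the site-form part of the fix is conditional on it. But the outcome list, aims and Table 3 are fixed here, and the claims row is limited to four symptoms.

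**The operative aim is tolerability.** Secondary aim 2 is so worded, and its outcomes match it. The broader statement on harms still stands in Section 1.1.

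**The benefit is limited.** The 0.19% limit is about 187 times the only arrhythmia rate in the document, and a weak effect on the composite is true of any rare component. Inpatient claims need not record an out-of-hospital sudden death or suicide, and the protocol names no source for certified cause of death. All of this stands. It rules out presenting the count as a powered safety test or as a full account of the fatal events.

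**Conclusion.** The point holds in a limited form. The protocol declares a purpose of comparing harms and names possibly fatal arrhythmia and suicidal behavior. It then fixes an adverse-event comparison that reaches these events by arm only as unattributed parts of all-cause hospitalization and death, apart from self-reported ideation and anything volunteered under the open category. Those totals are uninformative about a cause-specific excess: the composite hazard ratio moves by about 2% at most for an assumed excess of up to 1%.

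A reader might infer that the primary analysis is compromised. It is not: the all-cause composite is a legitimate pragmatic outcome, its event count and power reproduce, and the non-inferiority conclusion does not depend on cause. The excess rates, the background rates implied by the illustrative counts and the Medicare coverage are assumptions. The reading of the outcome list is not. Severity is low: a cheap improvement to the harms comparison.

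**What to change.** Extend the Table 3 adverse-event claims row with a pre-specified code list for (a) ventricular arrhythmia or cardiac arrest and (b) suicide attempt or self-harm. Apply it to the Medicare inpatient claims already requested under Section 2.3. Report by-arm counts with confidence intervals under Secondary aim 2, labelled descriptive.

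If site reports of hospitalization or death do not already carry it, add the recorded principal diagnosis, not the site's judgment of drug attribution. Show those counts by arm, separately from the claims counts, and include them in the DSMB reports. Leave the primary outcome and sample size unchanged.

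**Cost:** one code list, one descriptive table and, if absent, one item on the site report.

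**Downsides to state with the table:**
- Counts will be small and unpowered, and cannot exclude excesses of 0.1% to 0.2%.
- Claims cover the Medicare subset only.
- Out-of-hospital sudden deaths and suicides will largely be missed by inpatient claims.
- Capture after the first primary event is incomplete.
- Site coding is open-label and unadjudicated, and cardiac arrest may be recorded as the terminal event of a respiratory death.

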There is also uncertainty in the potential long-term risk of promoting macrolide-resistant organisms when instituting chronic macrolides such as azithromycin in clinical populations. Data from the three azithromycin studies (MACRO trial³⁷, COLUMBUS trial²⁷, and BACE trial⁶⁹; Table 2) indicate that the prevalence of macrolide-resistant pathogens was already fairly high prior to initiating therapy. In the BACE trial, sputum samples were obtained in fewer than 20% at the end of treatment and follow-up periods in both groups, so no conclusions were made on shifts in bacterial resistance⁶⁹. The incidence of macrolide-resistant pathogens among participants not colonized at baseline were about twice the incidence in the azithromycin vs. the placebo group (81% vs. 41%, $P<0.0001$) in the MACRO trial³⁰ and higher in the placebo groups in the COLUMBUS trial²⁷ (6% vs 24%, $P=0.036$). Note, however, that in the larger MACRO trial, testing for macrolide resistance was not performed in many patients at baseline or at follow-up, so the true difference in macrolide resistance across groups may be higher or lower than reported.

Protocol Version 4.0

Table 2: Macrolide resistance

	Study regimens (Study name, journal, year)	Azithromycin 250 mg/day vs. placebo X 12 mos; MACRO trial, NEJM 2011	Azithromycin 500 mg vs. placebo 3x/wk X 12 mos; COLUMBUS trial, Lancet Resp Med 2014	Azithromycin 250 mg every 2 days vs. placebo X 3 mos; BACE trial, AJRCCM 2019
	Azithromycin vs placebo groups, n	558 vs. 559	47 vs. 45	147 vs. 154
Baseline data	Prevalence of respiratory pathogens, n (%)	79/558 (14%) vs. 83/559 (15%)	7/22 (32%) vs. 6/20 (30%)	6/109 (5.5%) vs. 2/103 (1.9%)
	Prevalence of macrolide resistance among those with respiratory pathogens, n (%)	23/44 (52%) vs. 28/49 (57%)	5/7 (71%) vs. 4/6 (67%)	37/110 (33.9%) vs. 30/109 (29.1%)
Follow-up data	Incidence of resp pathogens, n (%)	66/558 (12%) vs. 172/559 (31%); p<0.0001	4/25 (16%) vs. 12/27 (44%); p=0.03	4/24 (16.7%) vs. 3/22 (13.6%)
	Incidence of macrolide resistance among those with data on newly acquired respiratory pathogens, n (%)	38/47 (81%) vs. 44/108 (41%), p<0.0001	3/4 (75%) vs. 11/12 (92%); p=0.38	0/23 (0.0%) vs. 1/21 (4.8%)

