4.3. Potential Risks

During this study, participants will continue to receive their usual care for COPD as per their treating physician. There are no additional evaluation procedures that patients will undergo to participate in the study. Patients will be asked to provide some information on their health history and current health status that is routinely collected in the process of medical care of patients with COPD. There are no significant physical risks from these procedures. As with all medical information, there is always the risk of psychological distress if PHI is not held confidential within the wishes of the participant. In order to minimize this risk, EHRs are held in HIPAA-2 compliant password-protected databases, and written information is stored in locked files or file-rooms when not attended by study personnel. Medical information is provided to treating sources consistent with HIPAA guidelines. If any medical illness requiring treatment is discovered during the collection of data for the course of this study protocol, individuals will be referred to their primary care providers for further evaluation and treatment.

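### Macrolide resistance is specified as positive sputum cultures only, with no count of cultures taken or tested, so the arm comparison is open to bias from differential testing

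*Protocol*

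**What the plan says.** The outcome appears in three places in the Protocol, each time as positive findings only.

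- PICOTS table, Outcomes, under adverse events: "microbiology cultures in which macrolide-resistant organisms were identified in sputum (sole: EHR". The word before EHR may be a misprint for the label used in neighbouring entries; on either reading the EHR is the only source listed.
- Section 2.2, text: Site Coordinators submit "microbiology cultures in which macrolide-resistant organisms were identified in sputum from the EHR via ad hoc and end-of-study reports on the Investigator Portal".
- Section 2.2, Table 3: a row headed "Adverse event (microbiology cultures of macrolide resistant organisms in sputum", with the Investigator Portal as source and end of study as the time point.

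No part of the Protocol asks how many participants were cultured, how many cultures were taken, how many grew a pathogen, or how many isolates were tested for macrolide susceptibility.

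Two design features decide which cultures exist. No sputum sampling is scheduled: section 2.2 plans no in-person study visits beyond normal practice, and section 4.3 says "There are no additional evaluation procedures that patients will undergo to participate in the study". The people who order and report cultures also know the treatment. Section 1.2 states "Once a patient is assigned to receive a treatment, the clinician, Site Coordinator and patient will all be unmasked", and section 2.1 says the same.

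**The concern.** A count of resistant cultures is the product of three things: how often a pathogen is present and recovered, how often an isolate is tested for susceptibility, and how often a tested isolate is resistant. Only the last is resistance in the usual microbiological sense. Treatment may change the first, and open-label clinical habit may change the frequency of both culture and testing. With the numerator alone, an arm difference, or the absence of one, cannot be assigned to any of the three.

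Section 1.1 names the promotion of resistant organisms as an uncertainty of long-term macrolide use, and says RELIANCE seeks to compare the harms of both drugs in routine settings. Its Table 2 presents earlier trials with denominators that the RELIANCE item does not call for. The same section notes that BACE drew no conclusion on resistance because few participants gave sputum late in the study. From the data items it specifies, RELIANCE could not report the corresponding proportion.

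**Working it through.** **Inputs** (Protocol section 1.1, Table 2, azithromycin vs placebo)

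- MACRO randomised: 558 vs 559.
- MACRO newly acquired pathogens: "66/558 (12%) vs. 172/559 (31%); p<0.0001".
- MACRO resistant among new pathogens with data: "38/47 (81%) vs. 44/108 (41%), p<0.0001".
- COLUMBUS randomised: 47 vs 45; resistant among new pathogens with data: "3/4 (75%) vs. 11/12 (92%); p=0.38".

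**Step 1. Reproduce the stated figure.** 38/47 = 80.9% and 44/108 = 40.7%. The risk ratio is 0.8085/0.4074 = 1.98 (log-normal 95% CI 1.52 to 2.59), Fisher p about 0.000004. This agrees with Table 2.

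**Step 2. Same positives, per randomised participant.** 38/558 = 6.8% and 44/559 = 7.9%. The risk ratio is 0.0681/0.0787 = 0.87 (95% CI 0.57 to 1.31), chi-square p = 0.50. The twofold excess is gone, and the interval shows no clear direction.

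**Step 3. Where the contrast comes from.** Take the pathogens with data as a subset of the new pathogens, as the table's row labels indicate. Then

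resistant/randomised = (new pathogen/randomised) × (tested/new pathogen) × (resistant/tested).

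| Factor | Azithromycin | Placebo | Ratio |
|---|---|---|---|
| New pathogen per randomised | 66/558 = 11.8% | 172/559 = 30.8% | 0.384 |
| Tested per new pathogen | 47/66 = 71.2% | 108/172 = 62.8% | 1.134 |
| Resistant per tested | 38/47 = 80.9% | 44/108 = 40.7% | 1.985 |
| Product | 6.8% | 7.9% | 0.87 |

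The first factor drives the contrast: fewer new pathogens on azithromycin. Testing completeness slightly favoured azithromycin. If untested isolates had been resistant at the same rates, full testing would give 66 × 38/47 = about 53 of 558 (9.6%) against 172 × 44/108 = about 70 of 559 (12.5%), still lower on azithromycin.

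**Step 4. COLUMBUS.** 3/4 vs 11/12 gives chi-square p = 0.38, as in Table 2. Over all randomised, 3/47 = 6.4% and 11/45 = 24.4%. These match the 6% and 24% in the text of section 1.1, which are given there with p = 0.036. I obtain 0.016 by chi-square, 0.034 with continuity correction and 0.020 by Fisher. The direction is the same on both denominators, but the apparent strength of evidence is not.

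**Step 5. How far testing alone could move a RELIANCE count.** Assumptions, not Protocol figures: 1,600 per arm, 20% of roflumilast participants with a tested isolate, and MACRO resistance rates (azithromycin 38/47; roflumilast given the placebo rate, 44/108). Expected positives = 1,600 × fraction tested × resistance rate, so roflumilast has 1,600 × 0.20 × 0.4074 = 130.4.

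| Azithromycin fraction tested | Expected positives | Ratio to roflumilast |
|---|---|---|
| 8% | 103.5 | 0.79 |
| 10% | 129.4 | 0.99 |
| 20% | 258.7 | 1.98 |
| 30% | 388.1 | 2.98 |
| 40% | 517.4 | 3.97 |

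Resistance per tested isolate is the same in every row. The counts are equal when the ratio of tested fractions is 0.4074/0.8085 = 0.50; in MACRO that ratio was (47/558)/(108/559) = 0.44. If resistance per isolate were equal in the two arms, the count ratio would simply equal the ratio of tested fractions.

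**The case against.** Several points on the other side stand.

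- **MACRO does not demonstrate testing bias.** It was placebo-controlled, and step 3 traces its contrast to pathogen acquisition. A reader might infer that unblinded testing has been shown to distort this outcome. The Protocol contains no figure for that. It is a risk of unknown size and direction created by the open-label design.
- **The per-randomised rate is a legitimate measure.** It is the as-randomised chance that a resistant organism is found. Resistance per isolate conditions on acquiring a pathogen, which treatment may alter, and section 3.3 itself cautions against analyses that rely on post-randomisation variables. A reader might infer that the plan would give an answer in the wrong direction. Tables 1 and 2 of the Protocol do not support this: the two measures answer different questions, and 0.87 (0.57 to 1.31) establishes no direction.
- **Section 1.1 does not describe the same fault.** Its caution about MACRO concerns tests not performed in many patients. MACRO had its denominators and its result was still called uncertain.
- **Silence is not prohibition.** Table 3 lists data domains rather than form fields, the portal form is not shown, and section 2.2 lets coordinators submit other relevant information. It would go too far to say that the denominators cannot be recovered; the Protocol simply does not call for them.
- **The outcome is not central.** Secondary aim 2 in section 1.2 does not list resistance, nor does the opening summary of secondary endpoints, and section 3.2 treats secondary reports as hypothesis generating.

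None of this answers the core point. The per-randomised rate compares the arms fairly only if cultures are taken and tested alike in both, and the specified data neither secure that nor allow it to be checked. A statistical analysis plan, if one exists, can choose a denominator but cannot supply one from items that were never requested.

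**Conclusion.** The point holds as a limitation in what is collected for a secondary safety outcome. As specified, the resistance comparison is open to bias from differential testing and cannot separate testing frequency, pathogen suppression and resistance. The Protocol's own data show that the choice of denominator is consequential: a risk ratio of 1.98 per tested new pathogen against 0.87 per randomised participant in MACRO, from the same 38 and 44 positives.

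The size of any testing bias in RELIANCE is unknown. The range of 0.79 to 3.97 in step 5 is conditional on assumed testing fractions and borrowed resistance rates. The verdict also assumes that the site forms collect no more than the Protocol describes. The primary non-inferiority test is unaffected, and the change below is a cheap improvement rather than a condition for the trial's validity.

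**What to change.** At the end-of-study EHR review, record for every participant, including those with none:

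1. the number of sputum cultures taken;
2. the number growing a pathogen;
3. the number tested for macrolide susceptibility;
4. the number resistant.

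Amend the PICOTS entry, the section 2.2 text and the Table 3 row to match. Keep the per-randomised rate. Report resistance per tested participant and per tested isolate beside it, labelled descriptive, and compare testing frequency by arm so that readers can judge how much of any difference could come from testing.

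The cost is extra abstraction time at the sites, for up to 3,200 participants followed for up to 36 months; the Protocol gives no basis for estimating the hours. No patient procedure is added and the pragmatic design is unchanged. The added counts reveal differential testing but do not remove bias from discretionary culture and testing, and the report should say so.
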